### **Step-By-Step Instructions for the Placement of Mepitel Film:**

Mepitel Film may be applied by nursing support, or trained staff. Application is easiest with two individuals, though possible with one.

Patient should be positioned supine with arms up, similar to the way they are positioned for treatment.

Skin should be clean, free of lotions at the time of film placement. If needed skin can be cleansed with water only. Please do not use baby wipes, or soap to clean the skin.

Determine size of Mepitel Film needed prior to beginning application.

Pre-cutting the Mepitel Film to the appropriate size will facilitate ease of placement. It is often easier to cut one large film into two halves to have better adherence to the skin and contours of the breast.

If applying with two people, position one person on each side of the patient/exam table.

Carefully remove the backing from the Mepitel Film. Avoid allowing it to stick to itself (which it has a tendency to do).

Place one end of the film onto the patient's skin while holding the opposite end up, avoiding contact with the skin. Slowly press the film onto the patient's skin starting from the applied end working toward the opposite end. Care should be taken to work slow, cover every contour, and avoid any air bubbles under the film.

After film is applied, remove the paper border taking care to press down edges of the film as the border is removed.

Remove any air bubbles using your fingertips to work the bubbles to the edge of the film.

Tips for covering reconstructed breast: If the film is going to crease or is causing an overlap, cutting "darts" in at the corners allows the film to lie flat.

Overlap when seaming two pieces of Mepitel is acceptable and may be preferred so that seams do not come apart creating an open seam. Minimize overlap to less than 1 cm.

While showering with Mepitel in place, recommend draping a hand towel over the patient's ipsilateral shoulder, so the water does not beat directly on the Mepitel Film. Encourage patient not to shower for 24 hours after placement, to increase likelihood of adherence.

Of note, the small piece of Mepitel Film applied to the contralateral side should extend posteriorly enough that the swinging of the patient's arm does not cause the posterior border to roll up. This is generally well accomplished with a single, uncut small piece.

Optional: Immediately following placement of the film, a warm blanket may be applied over Mepitel Film field and allowed to stay in place for 2-3 minutes. This may help with adherence and bring other unseen air bubbles to the surface.

Mepitel Film is typically applied using a patchwork approach. Based on the Mayo institutional experience, patients do not experience pain during application or removal of the Mepitel Film. If, after application of the Mepitel Film, the patient develops worsening pruritus or rash that, in the treating provider's opinion, is inconsistent with radiation related toxicity, and consistent with a film intolerance or allergy, the Mepitel Film may be removed. This is an unusual occurrence affecting less than 10% of patients, and typically happens within the first week following application. These patients should then be treated according to the institutional standard of care, and the film removal documented (see onstudy form in Medidata Rave). Should any patient develop pain secondary to film removal on this study, our recommendation is to proceed with conservative management with acetaminophen or ibuprofen as needed. If a patient develops moist desquamation under the Mepitel Film, the area of film immediately overlying the affected area of skin may be removed, and the treating provider should direct treatment of the moist desquamation according to their institutional standard of care. Mepitel Film should not be reapplied to

this area; however, it should remain in place over the remainder of the skin that is not affected by moist desquamation.

# 7.3 Radiotherapy

All radiation specific parameters should be recorded on the dosimetry form and submitted to IROC Rhode Island. Radiation will be conducted at the registering institution.

**Dose:** All patients will receive conventionally fractionated photon-based radiation. Acceptable regimens include:

- a) 50 Gy (2 Gy per fraction x 25 fractions)
- b) 50.4 Gy (1.8 Gy per fraction x 28 fractions)

**Volumes:** Primary treatment volumes should include the chest wall or reconstructed breast. Specific parameters defining the GTV, CTV, and PTV volumes are not defined in this trial, should be defined by the treating provider. Inclusion of the supraclavicular fossa, and/or axilla and/or internal mammary nodal basin is typical in the post mastectomy radiotherapy setting. Nodal radiation volumes and coverage are left up to the discretion of the treating physician.

**Organs at Risk (OAR):** Skin is the single required defined OAR volume included on this trial. The skin contour should be designated as a 3mm extraction from the external body contour. The D1cc, V105, and V110 of the skin must be reported.

**Modality:** Acceptable modalities include:

- a) 3D-CRT
- b) IMRT (see Section 15.1.2)
- c) Hybrid 3D + IMRT

**Energy:** Megavoltage photon beam energies  $\geq$  4MV are required. Electron beams require megavoltage energies. Proton therapy is not allowed on this trial.

**Boost:** The use of a sequential radiation boost to the chest wall, lymph nodes, or both, is allowed on this trial, provided it complies with the following parameters:

**Dose:** 10-16 Gy (1.8 Gy or 2 Gy per fraction)

**Modality**: Photons or Electrons

**Bolus:** The use of tissue equivalent bolus is allowed on this trial. The specific bolus technique is directed by the treating physician according to the institutional standard of care.

**Simulation:** A treatment planning CT following mastectomy and immediate reconstruction (if applicable), in the treatment position is required to define organs at risk (OAR). Simulation and treatment must be performed with the patient positioned in the supine position. Acceptable immobilization includes, but is not limited to, breast boards, alpha cradle, vac loc, wing boards.

**Reconstruction considerations:** For patients with fluid filled expanders in place at the time of radiation planning, the amount of fluid is at the discretion of the treating physician; however, the volume should remain constant throughout radiation. If a contralateral expander is in place at the time of simulation, it may be deflated at the discretion of the treating physician; however, the volume of the contralateral expander should not change during the course of planning and radiation if it impacts doses to the treatment volumes or OAR.

#### 7.3.1 Radiation Therapy Quality Assurance

A pre-treatment central review or Radiation Therapy Quality Assurance process is not required. Submission of treatment plans via TRIAD as DICOM RT is required within 7

days following the completion of radiation therapy. Use of TRIAD requires several preliminary steps (see Section 4.2 and Section 6.3). Additional information is available at:

All data should be submitted by the 7-14-day follow-up visit.

Within one week of the completion of radiotherapy, the following data should be submitted for review:

- RT treatment plan including CT, structures, dose, and plan files. These items are included in the digital plan.
- Digitally reconstructed radiographs (DRR) for each treatment field. Submission of DRR's is not required for IMRT.
- Treatment planning system summary report that includes the monitor unit calculations, beam parameters, calculation algorithm, and volume of interest dose statistics.
- RT-1 Dosimetry Summary Form
- The RT-2 Radiotherapy Total Dose Record Form
- A copy of the patient's radiotherapy record including the prescription, and the daily and cumulative doses to all required areas.

Any items listed above that are not part of the digital submission may be included with the transmission of the digital RT data or submitted separately via e-mail to

Ouestions regarding the dose calculations or documentation should be directed to:

# **Compliance Criteria**

Specified Radiation Dose

Variation Acceptable: Total dose or dose per fraction is >5% but <10% of the specified protocol dose.

Deviation Unacceptable: Total dose or dose per fraction deviates by more than 10% from the specified protocol dose.

# 8.0 DOSE AND TREATMENT MODIFICATIONS, UNBLINDING

# 8.1 Ancillary Therapy, Concomitant Medications, and Supportive Care

# 8.1.1 Ancillary Therapy

Patients should not receive any other treatment which would be considered treatment for the primary neoplasm or impact the primary endpoint, other than endocrine treatment or HER2 directed therapies as allowed in Section 3.2.9.

# 8.1.2 Supportive Care

Patients should receive full supportive care while on this study. Patients randomized to the standard of care arm may use any topical intervention the treating provider deems appropriate, including, but not limited to aqueous creams, petroleum ointments, aloe vera, acetic acid soaks, prescription interventions such as mometasone or lidocaine, and wound care interventions such as Xeroform gauze or silvadene. All products used should be recorded (see Appendix IV).

Patients randomized to the Mepitel Film arm, should not apply any of the aforementioned products over the area where Mepitel Film is in place. For areas of adjacent skin not covered by Mepitel Film, any of the aforementioned products may be applied, and should be recorded (see Appendix IV). If, during the course of treatment, the Provider deems it medically necessary to remove the Mepitel Film, or if the patient is experiencing unacceptable adverse events or intolerance requiring the removal of Mepitel Film, full supportive care is recommended at the direction of the treating physician. This includes, but is not limited to, any of the aforementioned products.

Any patients who require oral medications for pain, should be offered appropriate symptom management according to their treating physician.

Any barrier films intended to be used prophylactically, in a similar manner to Mepitel Film, (i.e. Mepitel One, Cavilon no sting Barrier Film, etc.), are not allowed on this study. This does not include barriers used in the treatment of symptomatic dermatitis, such as Xeroform gauze, which are allowed for symptom management.

# **8.1.3** Radiation Dose and Treatment Modifications

CTEP- AERS reporting may be required for some adverse events (See Section 9.0)

PRO-CTCAE data should not be used for determining dose delays or dose modifications or any other protocol-directed action.

Radiation doses should not be modified. Compliance with the protocol will require acceptable radiation modalities and conventionally fractionated treatments, as defined in Section 7.0. Patients may occasionally require treatment breaks; however, Mepitel Film should not be removed during these treatment breaks, and breaks should be kept to a minimum. Treatment breaks up to 5 treatment days will be considered acceptable. Treatment breaks greater than 5 treatment days are considered unacceptable and should be strongly discouraged.

#### 9.0 ADVERSE EVENTS

The prompt reporting of adverse events is the responsibility of each investigator engaged in clinical research, as required by Federal Regulations. Adverse events must be described and graded using the terminology and grading categories defined in the NCI's Common Terminology Criteria for Adverse Events (CTCAE), Version 5.0. The CTCAE is available at Attribution to protocol treatment for each adverse event must be determined by the investigator and reported on the required

treatment for each adverse event must be determined by the investigator and reported on the required forms. Please refer the NCI Guidelines: Adverse Event Reporting Requirements for further details on AE reporting procedures.

Clinician graded CTCAE is the AE safety standard. PRO-CTCAE items are to complement CTCAE reporting. Patients will respond to PRO-CTCAE items, but no protocol directed action will be taken. The specific PRO-CTCAE items for this protocol can be found in Appendix VII. PRO-CTCAE is not intended for expedited reporting, real time review or safety reporting.

Update #03

# 9.1 Routine Adverse Event Reporting

Adverse event data collection and reporting, which are required as part of every clinical trial are done to ensure the safety of patients enrolled in the studies as well as those who will enroll in future studies using similar agents. Adverse events are reported in a routine manner at scheduled times according to the study calendar in Section 5.0.

**Solicited Acute Adverse Events**: The following adverse events are considered "expected" and their presence/absence should be solicited, and severity graded at baseline, weekly while on treatment, at the 7-14-day post-treatment follow-up, and at the 3-month, 6-month, 1 year and 2-year post-treatment follow-up visits by CTCAE v5.0.

CTCAE v5.0 Term	CTCAE v5.0 System Organ Class (SOC)	PRO-CTCAE term	
Dermatitis radiation	
 
Injury, poisoning and procedural complications
 
	• Itching	
Rash acneiform	Skin and subcutaneous tissue disorders	
 
Radiation skin reaction
 
	
Rash maculo-papular	Skin and subcutaneous tissue disorders	General pain	
• Pruritus	Skin and subcutaneous tissue disorders	Breast swelling and tenderness	
Skin infection	Infections and infestations		

Symptomatic Adverse Events reported by patients through PRO-CTCAE are not safety reporting and may be presented with other routine Adverse Event data.

**Solicited Chronic Adverse Events**: The following adverse events are considered "expected" and their presence/absence should be solicited, and severity graded at the 3-month, 6-month, 1 year and 2-year post-treatment follow-up visits by CTCAE v5.0.

CTCAE v5.0 Term	CTCAE v5.0 System Organ Class (SOC)		
Superficial soft tissue fibrosis	Musculoskeletal and connective tissue disorders		
Fibrosis deep connective tissue	Musculoskeletal and connective tissue disorders		

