Baseline physician and patient reported surveys, including the mRISRAS, PRO-CTCAE and CTCAE toxicities will be completed prior to the start of radiation, as well as weekly while on treatment. Mepitel Film will be applied to the breast/chest wall by trained providers and changed as needed throughout treatment with a minimum frequency of once every two weeks. Based on our institutional experience, patients do not experience pain during application or removal of the Mepitel Film. Should any patient develop pain secondary to film application or removal on this study, our recommendation is to proceed with conservative management with acetaminophen or ibuprofen as needed. After completion of radiation, two additional sets of photographs will be obtained; one prior to the removal of Mepitel Film, and the second at least one hour after the removal of the Mepitel Film. These latter photographs will be used for analysis of the blinded secondary endpoint as outlined below. For patients randomized to the standard of care arm, only one set of photographs will be obtained immediately following completion of radiation therapy. A second set of skin swabs will also be obtained immediately after completion of radiation for all patients who provide their consent to participate in the optional study (following removal of the Mepitel Film for patients on the Mepitel Film arm) and all swabs will be frozen at -80°C for future analysis. The first follow-up at 7-14 days is important given the maximum degree of radiation dermatitis frequently occurs at 7-14 days post treatment. By the three-month follow-up appointment all patients would be expected to have achieved a resolution

of the acute effects of radiation dermatitis. Six-month, one year, and two-year post-treatment follow-up visits will be included to also evaluate chronic skin toxicities including telangiectasia, hyperpigmentation, skin and soft tissue fibrosis, and the rate of reconstruction failure/revision. Surveys and photographs for the assessment of acute toxicities will also be obtained at all follow-ups, whereas the chronic toxicities will be evaluated starting at the three-month follow-up.

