# 13.5 Statement for Secondary Endpoints

# 13.5.1 Secondary Endpoints

There are six secondary endpoints:

- 1. Centralized, blinded provider-completed mRISRAS scores obtained from a blinded grading of the photographs taken at the end of radiation therapy.
- 2. The serially measured non-blinded institutional provider-completed mRISRAS scores obtained at baseline (i.e. prior to the start of radiation), during weekly radiation therapy, at  $10 (\pm 4)$  days post-radiation therapy, and at 3-months post-radiation therapy.
- 3. The serially measured combined patient- and provider-completed mRISRAS scores obtained at baseline (i.e. prior to the start of radiation), during weekly radiation therapy, at  $10 (\pm 4)$  days post-radiation therapy, and at 3-months post-radiation therapy.
- 4. Time to biopsy proven local and/or regional failure.
- 5. Acute adverse events.
- 6. Chronic radiation therapy-related adverse events including skin and soft tissue fibrosis, telangiectasia, and hyperpigmentation.

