There are two other secondary endpoints that will be evaluated, and both are related to safety. The analysis of these safety endpoints will be based on the safety population, defined as all patients who initiated radiation; further the safety endpoints will be analyzed according to the intervention actually received. The constellation of acute and chronic adverse events (AEs) as scored using the National Cancer Institute Common Terminology Criteria for Adverse Events, v5.0 (CTCAE v5.0) will be summarized within arms by reporting the number and percentage of patients. Specifically, to evaluate the AE profiles associated with each arm, the maximum grade for each type of AE will be recorded for each patient and frequency tables will be reviewed to determine overall patterns. Additionally, the proportion of radiation dermatitis and skin and soft tissue fibrosis using NCI CTCAE v5.0 will be estimated within arms with the exact 95% confidence interval. Given the NCI CTCAE Version 5.0 scales for telangiectasia and hyperpigmentation are developed for total body surface area, they are not applicable to this study. As such, hyperpigmentation and telangiectasia will be evaluated on a 4-point scale, reflecting none, mild, moderate, and severe, and the corresponding number and percentage of patients reporting each will be presented according to arm. To evaluate the impact of chest wall separation on the constellation of AEs, we will display the AE profiles according to chest wall separation (> 25 cm; \le 25 cm) within each arm; additionally, other clinically meaningful separation thresholds will be explored depending on the distribution of the chest wall separation measurements.

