#### APPENDIX V NON-CTCAE TOXICITIES

Please complete at baseline prior to radiation therapy, weekly while on treatment, and at the 7-14 day, 3-month, 6-months, 1 year and 2-year post treatment follow up visits.

1) Provider assessment of Hyperpigmentation and Telangiectasia. Circle appropriate grade.

(Grade: 1 = none, 2 = mild, 3 = moderate, 4 = severe).

Hyperpigmentation: 1 2 3 4

Telangiectasia 1 2 3 4

2) Provider assessment of reconstruction complications

Did the patient experience a reconstruction complication, defined as wound dehiscence, wound infection requiring the administration of oral or IV antibiotics, mastectomy skin flap necrosis, reconstructive flap necrosis not resulting in complete loss of flap, capsular contracture, or implant leakage/rupture/deflation? Circle appropriate response.

Yes / No

If yes, specify type of complication

Date of complication \_\_\_\_\_

3) Provider assessment of reconstruction failure.

Did the patient experience a reconstruction failure, defined as loss of autologous reconstruction/flap, implant explantation, or unplanned expander removal without immediate replacement? Circle appropriate response.

Yes / No

If yes, specify type of failure\_\_\_\_\_

Date of failure \_\_\_\_\_

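### Soft-tissue fibrosis, named in secondary endpoint 6, has no pre-radiation grade, so fibrosis left by surgery can enter a radiation-related endpoint

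*Combined protocol and SAP*

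**What the plan says.** Section 13.5.1 lists as its sixth secondary endpoint "Chronic radiation therapy-related adverse events including skin and soft tissue fibrosis, telangiectasia, and hyperpigmentation".

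Section 9.1 sets two solicitation schedules. The five acute terms (radiation dermatitis, two rash terms, pruritus, skin infection) have "severity graded at baseline, weekly while on treatment, at the 7-14-day post-treatment follow-up" and at the later visits. The chronic list holds "Superficial soft tissue fibrosis" and its deep connective tissue counterpart, and these have "severity graded at the 3-month, 6-month, 1 year and 2-year post-treatment follow-up visits by CTCAE v5.0". The Section 5.0 calendar marks the chronic row only in the column running from 3 months to 2 years. Section 1.4 states that "the chronic toxicities will be evaluated starting at the three-month follow-up".

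Appendix V, the form for hyperpigmentation, telangiectasia and reconstruction events, is headed "Please complete at baseline prior to radiation therapy, weekly while on treatment", followed by the follow-up visits. Fibrosis is not on that form.

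For analysis, Section 13.5.2 tabulates each patient's worst grade per event type and adds that "the proportion of radiation dermatitis and skin and soft tissue fibrosis using NCI CTCAE v5.0 will be estimated within arms", with exact 95% intervals. It mentions no baseline grade, no exclusion of prevalent cases, no use of attribution and no visit window for the chronic summaries.

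**The concern.** Every patient has had a mastectomy, and Section 13.6.2 expects 30-50% to have reconstruction. Some tissue firmness from surgery is plausible before the first fraction. If it is still there at a follow-up visit and is graded, it counts toward an endpoint whose title attributes it to radiation, and nothing in the planned analysis separates it from new fibrosis.

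At stake is how far the reported fibrosis rates can be interpreted. A rate that mixes surgical and radiation fibrosis overstates the second, and the mixture pulls the two arms toward each other. Section 13.9 reports fibrosis again in the African American and Hispanic subgroup, with about 18 control patients, where one pre-existing case moves the control proportion by 1/18 = 5.6 points. A baseline grade that was never taken cannot be recovered.

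A smaller point concerns the other two chronic items. Section 1.4 names telangiectasia and hyperpigmentation among the chronic toxicities that start at 3 months, while Appendix V collects them at baseline and weekly. Since Section 13.5.2 gives no window, it is not settled whether on-treatment grades enter the chronic summary.

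**Working it through.** The main check is textual. The places that could supply a pre-radiation grade are set side by side:

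| Item | Pre-radiation grade? | Source |
|---|---|---|
| Five acute CTCAE terms | Yes | Section 9.1 |
| Hyperpigmentation, telangiectasia | Yes | Appendix V |
| Capsular contracture (as a reconstruction complication, yes/no with type and date) | Yes | Appendix V |
| Superficial and deep fibrosis | No, first at 3 months | Sections 9.1, 5.0, 1.4 |

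Section 1.4 also says that CTCAE toxicities are collected before radiation, without naming terms. This does not fill the gap, because the same section defers chronic toxicities to 3 months. Of the items named in endpoint 6, fibrosis alone lacks a baseline.

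The plan states no fibrosis rate, so there is no figure to reproduce. The direction of the effect follows from simple algebra. Let b be the proportion with fibrosis before radiation, assumed equal in both arms and still gradable at follow-up, and let p be the incidence of new fibrosis among the rest.

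- Observed proportion = b + (1 − b) × p
- Observed difference between arms = (1 − b) × (p control − p film)
- Share of control cases that were pre-existing = b / observed control proportion

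All rates below are assumptions: p = 30% for control, p = 20% for film.

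| b | Control | Film | Difference (points) | Relative risk | Pre-existing share, control |
|---|---|---|---|---|---|
| 0% | 30.0% | 20.0% | 10.0 | 0.67 | 0% |
| 5% | 33.5% | 24.0% | 9.5 | 0.72 | 15% |
| 10% | 37.0% | 28.0% | 9.0 | 0.76 | 27% |
| 20% | 44.0% | 36.0% | 8.0 | 0.82 | 45% |
| 30% | 51.0% | 44.0% | 7.0 | 0.86 | 59% |

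For example, at b = 20% the control proportion is 0.20 + 0.80 × 0.30 = 0.44, the film proportion is 0.20 + 0.80 × 0.20 = 0.36, and the pre-existing share is 0.20/0.44 = 45%.

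Chance imbalance in b would also go unseen. With the 64 and 128 patients of Section 13.3 and an assumed b of 10%, ignoring stratification, the 95% range for the between-arm difference in b is ±1.96 × √(0.10 × 0.90 × (1/64 + 1/128)) = ±9.0 points.

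**The case against.** There are real safeguards. Section 9.0 requires the investigator to attribute each adverse event to protocol treatment, and the grid in Section 9.2 includes unrelated and unlikely. Section 6.1.3 collects operative notes and notes of post-operative or reconstruction complications at baseline. The calendar requires a history and physical before registration. Appendix V records capsular contracture from baseline. These give attribution something to rest on. They remain partial: none is a fibrosis grade, and Section 13.5.2 does not say that attribution restricts what is counted.

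A reader might infer that the plan classes surgical fibrosis as radiation-related. No section says so; the supported statement is that it can be counted. A reader might also infer that the calendar contradicts Appendix V on hyperpigmentation and telangiectasia. It need not. Footnote 1 attaches the non-CTCAE items to the acute row, which is marked weekly before radiation, as well as to the chronic row. What needs reconciling is the sentence in Section 1.4. That on-treatment pigmentation would be counted as chronic is possible but not stated, and Section 9.2 assigns the late form to events more than 90 days after last treatment.

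The consequence is also limited. Fibrosis is summarised within arms, no between-arm test is planned for it, and it lies outside the gatekept family. Section 13.9's worked interval is framed on grade 3+ acute toxicity, so it is not a fibrosis figure.

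Finally, Section 7.0 allows radiation from 21 days after surgery. An early baseline could capture resolving post-operative change, and counting only grades above it could hide radiation fibrosis of the same grade. This stands as a reason not to replace the raw maximum.

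**Conclusion.** The point holds in a limited form. No pre-radiation fibrosis grade is scheduled in either arm, and the analysis as written has no means of separating new from pre-existing fibrosis. The descriptive rates can be inflated in both arms and any descriptive film contrast diluted by the factor (1 − b). The documents give neither pre-radiation prevalence nor new incidence, so the size is unknown and the table shows only the pattern under assumed rates.

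It would be wrong to read this as a bias in favour of film. The schedule is the same in both arms and randomization is stratified by reconstruction, so no systematic direction is expected. Chance imbalance cannot be checked, however, and the safety analysis follows the intervention received. The primary endpoint and the three gatekept secondary endpoints are unaffected. This is a cheap improvement to a named secondary endpoint.

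**What to change.** 1. In Section 9.1, add both fibrosis terms to those solicited at baseline, and mark them in the pre-radiation assessment of the Section 5.0 calendar, in both arms.
2. In Section 13.5.2, keep the raw maximum grade. Beside it, report the proportion with a new or worsened grade relative to baseline at visits from 3 months onward, for fibrosis, hyperpigmentation and telangiectasia.
3. State in Section 13.5.2 that chronic summaries use only visits from 3 months onward, and whether attribution restricts what is counted.
4. Reconcile the Section 1.4 sentence on the start of chronic assessment with Appendix V.

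The cost is two extra items on a baseline adverse event form already completed at an existing visit, plus short text changes. Patients already treated will lack a fibrosis baseline and can be shown by raw grade only. For hyperpigmentation and telangiectasia, Appendix V already requires the baseline, so the added summary can cover them too. Because an early post-operative baseline may mask same-grade radiation fibrosis, the new-or-worsened summary should stand beside the raw maximum and not replace it.
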